### **Primary endpoints**

The number of breakthrough bleeding events over time requiring the use of alternate hemostatic therapy (bleed rate) related to the pseudotumor.

---

\* Hemostatic efficacy is defined as the rate of breakthrough bleeding related to the pseudotumor; which is defined as the number of bleeding episodes while on Hemlibra that require alternative hemostatic therapy.

The number of hospital admissions related to the pseudotumor.

The number of incidences of anemia requiring transfusion or intervention related to the pseudotumor.

The control of progression, stabilization or regression of the pseudotumor (ie, changes in size) as measured by yearly assessments including CT or MRI.

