### *Efficacy Analyses*

The primary outcome for this study is bleeding events specifically related to the pseudotumor over time; total bleeding events will also be recorded and analyzed. Hemostatic efficacy is defined as the rate of breakthrough bleeding related to the pseudotumor (the number of bleeding episodes while on Hemlibra that require alternative hematinic therapy). Sample size is determined based on clinical feasibility rather than statistical considerations, accounting for the likely possibility of very few bleeding events, the limited number of available subjects with hemophilia A and pseudotumor, and the need to collect sufficient data to assess safety and efficacy.

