## 5.6 Treatment Compliance

All subjects will either self-administer Hemlibra (emicizumab) in an at-home setting, or have Hemlibra (emicizumab) administered by a trained caregiver or healthcare provider (either at home or at a local physician's office) on a weekly basis.\* Agents required to treat a breakthrough bleed may also be self-administered by the subject or a caregiver in an at-home setting, except aPCC, which if approved by the Study Investigator may only be administered by a physician.

The following will be recorded by the subject in their patient diary:

- The date and time of Hemlibra (emicizumab) administration
- The exact dose of Hemlibra (emicizumab) administered
- Any adverse events, duration and actions taken

Additionally, the subject will record the following for all bleeding events

- The date and time of onset
- The anatomical location and severity
- The agent(s) used to control the bleed, the exact dose(s), the number of doses and the time(s) of administration
- The Study Investigator will determine whether the bleeding event was related to the pseudotumor based on a retrospective review of the clinical data

Should the subject be admitted to a hospital or medical facility this should be recorded as described in **Section 6.11.3**, as should any incidences of anemia that require transfusion or intervention. All surgeries or deaths should also be recorded. Medical details of these events should be transmitted to the IHTC within 7 days of their occurrence

The patient diary will be checked by the subject's local physician during the quarterly study visits that take place at their local facilities and transmitted to the IHTC at that time. The patient diary will be reviewed by IHTC staff during the annual and study close-out visits at the IHTC.

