### 6.2 Medical History/Demographics

The medical history of the subject will be obtained. Specific information will be recorded on the CRF relating to any prior or existing medical conditions/surgical procedures involving the following: Infectious Diseases (including viral infections, such as Hepatitis and HIV), Allergies, Metabolic/Endocrine/Nutritional, Hematopoietic, Musculoskeletal, Dermatologic, Head, Ears, Eyes, Nose, and Throat (HEENT), Breasts, Respiratory, Cardiovascular, Gastrointestinal/Hepatic, Genitourinary/Renal, Neurologic, and Psychiatric/Psychosocial.

Specific documentation for the following should be provided to the IHTC:

- Medical documentation of any prophylactic (FVIII or bypassing agent) therapy for at least 16 weeks, and up to 6 months if available, prior to entry into the study
- Medical documentation for the number of bleeding episodes (including location, severity, duration and treatment) for at least 16 weeks, and up to 6 months if available, prior to entry into the study. If available, the hemostatic agent, number of infusions and quantity of drug infused for each bleeding episode will be collected
- Medical documentation of any complications related to the pseudotumor (including any incidences of anemia, the need for PRBC transfusion or hospitalization) for 6 months prior to entry into the study

- Subjects with a history of an inhibitor should provide documentation of the inhibitor history including date of initial diagnosis of inhibitor, peak titer, and agent utilized for hemostatic control
- Medical documentation of ITI therapy for subjects with a history of a FVIII inhibitor and ITI, including current FVIII inhibitor titer
- Documentation of current concomitant medications and supplements
- Date of development or identification of pseudotumor and documentation of radiologic (CT and/or MRI) scans

Demographics (date of birth, race/ethnicity, gender, height, weight, etc) and vital signs (blood pressure, pulse, temperature, and respiratory rate) will also be collected.

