## 6.10 Efficacy and Quality of Life Assessments

The primary outcome for this study is bleeding events specifically related to the pseudotumor over time; total bleeding events will also be recorded and analyzed.

All bleeding events will be recorded in the patient diary along with the following:

- The date and time of onset
- The anatomical location and severity
- The agent(s) used to control the bleed, the exact dose(s), the number of doses and the time(s) of administration
- The Study Investigator will determine whether the bleeding event was related to the pseudotumor based on a retrospective review of the clinical data

The efficacy of Hemlibra (emicizumab) will be determined by comparing the incidence of bleeding events and use of alternate hemostatic medication on study to the incidences prior to study enrollment and by changes over time.

The following should also be recorded and transmitted to the IHTC within 7 days of their occurrence:

- The admission of the subject to a hospital or medical facility (described in **Section 6.11.3**)
- Incidences of anemia that require transfusion or intervention
- All surgeries or deaths
- Any other AEs or SAEs noted and recorded by a physician

The efficacy of Hemlibra (emicizumab) will be determined by comparing the incidence of hospitalization and anemia that require transfusion or intervention on study to the incidences prior to study enrollment and by changes over time.

The following should be acquired during study visit 2 (if they were not performed within 1 month of study entry and if they are not considered suitable for study purposes) and at every annual study visit and the study close-out visit:

- Radiology (CT and/or MRI) to observe change in the size of the pseudotumor over time (ie, the progression, stabilization or regression of the pseudotumor)

The efficacy of Hemlibra (emicizumab) will be determined by the change in the size of the pseudotumor over time (ie, the control of progression, stabilization or regression of the pseudotumor).

The following will be used to determine changes in quality of life and activity level:

- Haem-A-QoL and EQ-5D-5L will be completed following screening and at every annual study visit and the study close-out visit

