#### 6.10.1 Primary Endpoints

The primary endpoints are:

- The number of breakthrough bleeding events over time requiring the use of alternate hemostatic therapy (bleed rate) related to the pseudotumor
- The number of hospital admissions related to the pseudotumor
- The number of incidences of anemia requiring transfusion or intervention related to the pseudotumor
- The change in the size of the pseudotumor over time (ie, the control of progression, stabilization or regression of the pseudotumor) as measured by yearly assessments including CT or MRI

The study investigator will determine whether the reported event was related to the pseudotumor based on a retrospective review of the medical data (eg, bleed location, patient symptoms, etc).

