### 9.5 Primary Endpoints

The primary endpoints are:

- The number of breakthrough bleeding events over time requiring the use of alternate hemostatic therapy (bleed rate) related to the pseudotumor
- The number of hospital admissions related to the pseudotumor
- The number of incidences of anemia requiring transfusion or intervention related to the pseudotumor
- The control of progression, stabilization or regression of the pseudotumor (ie, changes in size) as measured by yearly assessments including CT and/or MRI

The study investigator will determine whether the reported event was related to the pseudotumor based on a retrospective review of the medical data (eg, bleed location, patient symptoms, etc).

Efficacy analyses will be performed based on the parameters listed above. As there is no control group or placebo in the study, the on-study data will be compared to that listed in the subject's

medical files prior to study enrollment. The efficacy analyses will exclude data acquired during the 4 loading doses (study visit 2). Analyses will be performed on a per-subject basis and in aggregate. Sub-analyses will be considered based upon the included study population.

Demographic and baseline characteristics for all subjects will be summarized using descriptive statistics for continuous variables and frequencies and percentages for categorical variables.

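### Are pre-study bleeds, admissions and anemia counted by a looser rule than the on-study events they are compared with?

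*Combined protocol and SAP*

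**What the plan says.** The primary bleed endpoint in section 6.10.1, worded the same way in 9.5, is "The number of breakthrough bleeding events over time requiring the use of alternate hemostatic therapy (bleed rate) related to the pseudotumor". It therefore carries two conditions, treatment and relatedness. The synopsis footnote defines hemostatic efficacy as a rate based on "the number of bleeding episodes while on Hemlibra that require alternative hemostatic therapy", which covers only time on the study drug.

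The comparison is set in two places. Section 9.5 states that "the on-study data will be compared to that listed in the" subject's pre-enrollment medical files. Section 6.10 determines efficacy by "comparing the incidence of bleeding events and use of alternate hemostatic medication on study to the incidences prior to study enrollment". Relatedness is an investigator's call; section 5.6, in its list of diary items, says "The Study Investigator will determine whether the bleeding event was related to the pseudotumor based on a retrospective review of the clinical data".

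For the baseline bleeds, section 6.2 requires "Medical documentation for the number of bleeding episodes (including location, severity, duration and treatment) for at least 16 weeks", extended to 6 months where available. For admissions and anemia it requires documentation of "any complications related to the pseudotumor (including any incidences of anemia, the need for PRBC transfusion or hospitalization) for 6 months". Sections 4.2 and 7.1 instead ask for any hospitalization and for red-cell transfusion over 6 months, without mention of the pseudotumor or of anemia as such.

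**The concern.** For bleeds, admissions and anemia, the pre-study record is the only reference outside the treatment period. No sentence says that a baseline bleed counts only if it was treated and related. The efficacy definition looks only at time on drug, and the relatedness call in 5.6 and 6.10 sits among on-study diary items. *Alternate* therapy also has no obvious meaning for a subject who was already on FVIII or a bypassing agent before entry. The wording of the treatment condition drifts as well: the synopsis efficacy paragraph has "the number of bleeding episodes while on Hemlibra that require alternative hematinic therapy", and the footnote to 2.2 has hematologic.

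The baseline scopes for admissions and anemia differ between 4.2/7.1 and 6.2, and neither reproduces the on-study anemia endpoint, which requires transfusion or intervention. Section 9.5 also words these two endpoints as numbers, although the two observation windows differ greatly in length. If a broad baseline were set against a narrow on-study count, part of any reported fall would come from the counting rule rather than the drug.

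**Working it through.** **Nothing to reproduce.** The sample size (about 10) rests on feasibility (9.2) and the analysis is descriptive (9.1). The plan states no bleed rate, effect size or test.

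**Size if the baseline were unfiltered.** Let s be the share of bleeds related to the pseudotumor and t the share treated. Neither is in the documents, so both are assumed. With no drug effect, the ratio of on-study to baseline rate is s × t:

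- 0.90 × 1.00 = 0.90, a false reduction of 10%
- 0.75 × 0.75 = 0.5625, or 44%
- 0.50 × 0.80 = 0.40, or 60%
- the same filters in both periods: 1.00, or 0%

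Under-recording in medical files acts the other way. If files held 80% of baseline bleeds (also assumed), the second case becomes 0.5625 / 0.8 = 0.70, or 30%.

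**Does the plan call for an unfiltered baseline?** Four places bear on this.

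1. In 9.5, the sentence just before the comparison bases the efficacy analyses on the endpoints listed there. Those are the treated, related events.
2. Section 9.6 repeats the same pre-study comparison for the treated bleed rate *unrelated* to the pseudotumor. If one unfiltered count served both comparisons, the null ratios would be s × t and (1 − s) × t. With s = t = 0.75 these are 0.5625 and 0.25 × 0.75 = 0.1875. Two non-overlapping kinds of bleed would both appear to fall with no drug effect. Comparing both rates with the files makes sense only if baseline bleeds are split by relatedness.
3. Section 6.10 words the bleed comparison alike for the two periods and names the use of hemostatic medication in both.
4. Section 6.2 collects location and treatment for each baseline bleed. Section 9.5 gives bleed location as an example of what the investigator uses to judge relatedness.

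**Admissions and anemia.** The scopes are nested. Pseudotumor-related admissions (6.2) are a subset of all admissions (4.2, 7.1). Related anemia of any kind (6.2) contains related anemia that needed transfusion or intervention. The endpoint is reached by selecting from the 6.2 record. Sections 4.2 and 7.1 are an eligibility requirement and a screening checklist, and collecting broadly before selecting at analysis is ordinary practice.

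**Number or rate.** For 10 subjects, with 4/52.18 = 0.077 years of loading removed:

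- baseline: 10 × 16/52.18 = 3.07 subject-years (bleeds, minimum) to 10 × 0.5 = 5.0
- on study: 10 × (2 − 0.077) = 19.2 to 10 × (4 − 0.077) = 39.2
- window ratio for admissions and anemia: 19.2/5.0 = 3.8 to 39.2/5.0 = 7.8

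Raw counts would mislead over such windows. However, 6.10 compares incidences, the study question in 3.1 asks about rates, and the bleed endpoint is itself labelled a bleed rate.

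**The case for a change.** The strongest case for a change is that all of this is inference. The relatedness sentence in 9.5 speaks of the reported event and does not name pre-study bleeds. Nothing states the treatment condition at baseline. Section 6.2 asks for agent, infusions and quantity only where available, so some baseline bleeds may be hard to classify. The person who judges relatedness knows the treatment period. With about 10 subjects and few bleeds expected, moving a handful of events matters even in a descriptive summary, and a clarifying sentence would cost little.

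It stands that no sentence expressly carries the filters back to baseline, and that 4.2/7.1 and 6.2 do not say which is the comparator. The implied bias does not follow. It needs a rule that the plan never states and that would make 9.5 and 9.6 incoherent together. Open-label judgment and patchy records come with a retrospective comparator; a definition sentence would remove neither.

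The side points carry little weight. Hematinic and hematologic are slips, because the endpoint lists consistently say hemostatic and 6.10.2 names the agents. For a subject on prophylaxis, treatment given for a bleed beyond the scheduled regimen is the natural reading of alternate therapy. The exemptions in 6.11.3.2d concern adverse-event reporting, and 3.1.4 has hospitalizations recorded in the CRF regardless. A check that does not depend on relatedness is already planned, since 6.10 has total bleeding events analyzed and compares bleeding incidence before and during the study.

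**Conclusion.** No change to the plan follows. What is missing is an explicit statement that the two periods are counted alike. Sections 9.5, 9.6 and 6.10 read together lead an analyst to that rule, and 6.2 supplies the location and treatment data to apply it. Counted that way, the difference in definition contributes a false reduction of 0%.

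The 10% to 60% range measures a reading the documents do not call for. It rests on assumed shares, and under-recording in medical files would offset some of it, so even the net direction is unknown. Pseudotumor size and on-study trends are untouched. Per-subject analysis (9.5) and subject data listings (9.1) also let a reader inspect individual baseline counts.

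The conclusion assumes that the analyst reads 9.5 together with 9.6, and that the 6.2 records are complete enough to classify most baseline bleeds.

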### 3.1.2 Second Study Visit [Hemlibra (emicizumab) Loading Doses]

The second study visit will take place at the IHTC up to 10 days after the initial screening visit. The purpose of the second study visit is to administer the 4 weekly loading doses of Hemlibra (emicizumab); acquire ADA data, vital signs (blood pressure, pulse, temperature, and respiratory rate) and weight; and complete baseline radiology.

Prior to the first loading dose, a banked plasma sample will be obtained to determine baseline anti-drug antibody levels for Hemlibra (emicizumab). Baseline radiology (CT and/or MRI) will also be obtained if not previously performed within one month of study entry or if provided scans are deemed inadequate to accurately assess the extent of the pseudotumor.

Subjects/caregivers will be instructed on how to inject Hemlibra (emicizumab) and how to recognize signs/symptoms of hypersensitivity (including anaphylaxis) and obtain emergency care in the event of such reactions occurring. The Study Investigator has the discretion to provide additional training or include additional observation (eg, after the fourth loading dose), if deemed appropriate, and each subject/caregiver will be able to ask any question he or she may have prior to being deemed capable of performing subcutaneous Hemlibra (emicizumab) injections. If, despite additional training, the investigator determines that the subject/caregiver is unable to inject Hemlibra (emicizumab), a trained and proficient caregiver or local healthcare provider should be identified to administer the prophylaxis injections.

The 4 loading doses will be administered once weekly for 4 weeks using the FDA-approved regimen (3 mg/kg once weekly by subcutaneous injection). Following the 4th loading dose a second banked plasma sample will be obtained to determine anti-drug antibody levels for Hemlibra (emicizumab). If the subject routinely uses an activity monitoring device and has consented to the use of data from that device during the study, then data from the time of informed consent will be collected.

During study visit 2 suitable quantities (to be determined by the Study Investigator) of Hemlibra (emicizumab) will be dispensed to the subject (see **Section 6.7**).

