## 7.2 Study Visit 2: Loading Doses

Study visit 2 will comprise 4 weeks during which the 4 loading doses of Hemlibra (emicizumab) will be administered. During study visit 2, baseline radiology (CT and/or MRI scan) will be acquired if they were not performed within 1 month of study entry and if they are not considered suitable for study purposes. The subject and/or caregiver will also be trained for self-infusion of Hemlibra (emicizumab) and trained to look for signs of adverse events.

Subjects/caregivers will be instructed on how to recognize signs/symptoms of hypersensitivity (including anaphylaxis) and obtain emergency care in the event of such reactions occurring. The Study Investigator has the discretion to provide additional training or include additional observation (eg, after the fourth loading dose), if deemed appropriate, and each subject/caregiver will be able to ask any question he or she may have prior to being deemed capable of performing subcutaneous Hemlibra (emicizumab) injections. If, despite additional training, the investigator

---

\* Vaccinations will not be charged to the study

determines that the subject/caregiver is unable to inject Hemlibra (emicizumab), a trained and proficient caregiver or local healthcare provider should be identified to administer the injections.

Subjects will be observed for a minimum of 30 minutes after the first three loading doses of Hemlibra (emicizumab).

Following each of the first 3 loading doses of Hemlibra (emicizumab), the site will call a subject who has a previous history of a clinically significant hypersensitivity reaction 24 hours after each dose to assess the status of the subject.

Additional precautions following each of these doses may also be considered, including having an extended observation period or IV access prior to dosing, etc. The Study Investigator may include these or other precautions, as deemed appropriate.

A subject utilizing a prophylactic FVIII regimen, a prophylactic bypassing agent regimen or ITI therapy must discontinue those regimens according to the schedule below and for the duration of the study.

- Subjects receiving FVIII prophylaxis must discontinue their FVIII prophylactic regimen immediately prior to their second loading dose of Hemlibra (emicizumab)
- Subjects receiving bypassing agent prophylaxis must discontinue their prophylactic regimen at least 24 hours prior to their first loading dose of Hemlibra (emicizumab)

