### 7.2.2 Day 0 Procedures

#### 7.2.2.1 *Pre-treatment*

- Measurement of vital signs (blood pressure, pulse, temperature, and respiratory rate) and weight
- Confirmation of eligibility
  - Subject should not have received aPCC or rFVIIa within 24 hours prior to study drug administration
  - Subject should not have an active bleeding event

- Subject should not have any other temporary or permanent exclusionary event (at the discretion of the Study Investigator)
- Subjects who are receiving FVIII ITI therapy must discontinue ITI at this time and ITI must remain discontinued for the duration of the study
- Assessment of concomitant medication and supplements
- Assessment of adverse events
- Banked plasma sample [baseline antidrug antibody levels for Hemlibra (emicizumab)] for testing at the central laboratory
- Other diagnostic procedures as needed and ordered by the Study Investigator and recommended by the standard of care

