## 12 APPENDIX 2: Schedule of Study Visits (per Subject)

Evaluation  Visit Window:	Study Visit 1		Study Visit 2*			Day 7  ±2 days			±2 we
	Day -10	Day -1†	Day 0		Post-treatment	Pretreatment	Treatment	Post-treatment	
	n/a	n/a	n/a						
	Screening		Pretreatment	Treatment	Post-treatment	Pretreatment	Treatment	Post-treatment	
Informed consent	X								
I/E criteria	X								
Demographics	X								
Medical history review	X								
Vital signs	X		X				X		
Weight	X		X				X		
Physical examination	X								
Haem-A-QoL & EQ-5D-5L	X								
Clinical lab tests (6.6.1)	X								
Concomitant medications	X		X	X	X	X	X	X	
AE assessment	X		X	X	X	X	X	X	
Eligibility	X		X	X					
ADA Hemlibra (emicizumab)			X						
Drug administration (loading dose)		X		X				X	
Cease BPA prophylaxis			X						
Cease ITI				X					
Cease FVIII prophylaxis							X		
Activity monitoring device (data acquisition)	X								

\* An adequate quantity of Hemlibra (emicizumab) will be dispensed during study visit 2 for the loading and maintenance doses. The quantity will be at the discretion of the Study Investigator and will depend on the storage capacity at the subject's home

† A minimum of 24 hours prior to first loading dose of Hemlibra (emicizumab)

Evaluation  Visit Window:	Study Visit 2*					
	Day 14  ±2 days			Day 21  ±2 days		
	Pretreatment	Treatment	Post-treatment	Pretreatment	Treatment	Post-treatment
Informed consent						
I/E criteria						
Demographics						
Medical history review						
Vital signs	X			X		
Weight	X			X		
Physical examination						
Haem-A-QoL & EQ-5D-5L						
Clinical lab tests (6.6.1)						
Concomitant medications	X			X		
AE assessment	X	X	X	X	X	X
Eligibility						
ADA Hemlibra (emicizumab)						X
Drug administration (loading dose)		X			X	
Activity monitoring device (data acquisition)						X

\* An adequate quantity of Hemlibra (emicizumab) will be dispensed during study visit 2 for the loading and maintenance doses. The quantity will be at the discretion of the Study Investigator and will depend on the storage capacity at the subject's home

	Month 3 Visit Window: ±2 weeks	Month 6 Visit Window: ±2 weeks	Month 9 Visit Window: ±2 weeks	Month 12 Visit Window: ±2 weeks	Month 15 Visit Window: ±2 weeks	Month 18 Visit Window: ±2 weeks	Month 21 Visit Window: ±2 weeks	Month 24 Visit Window: ±2 weeks
Visit @ local provider	X	X	X		X	X	X	
Visit @ IHTC				X				X
Activity monitoring device (data acquisition)	X	X	X	X	X	X	X	X
Subject study documentation (transfer to IHTC)	X	X	X	X	X	X	X	X

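### Read literally, the efficacy exclusion in 9.5 and 9.6 discards a baseline pseudotumor scan taken in study visit 2, and no procedure list requires that scan before the first dose

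*Combined protocol and SAP*

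**What the plan says.** Pseudotumor size is one of four primary endpoints. Section 6.10.1 words it as "The change in the size of the pseudotumor over time (ie, the control of progression, stabilization or regression of the pseudotumor", assessed on yearly CT or MRI; the first scheduled on-treatment scan is at month 12.

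The baseline scan is conditional. Section 3.1.2 has "Baseline radiology (CT and/or MRI) will also be obtained if not previously performed within one month of study entry" or if the available scans are inadequate. Section 7.2 has "During study visit 2, baseline radiology (CT and/or MRI scan) will be acquired", and 6.10 introduces the same item with "The following should be acquired during study visit 2". By 7.2, study visit 2 lasts 4 weeks, with loading doses on Days 0, 7, 14 and 21.

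Section 9.5 lists the size endpoint among its efficacy parameters and then applies two rules to all of them:

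- The comparator: "As there is no control group or placebo in the study, the on-study data will be compared to that listed in the" subject's pre-enrollment medical files.
- The exclusion: "The efficacy analyses will exclude data acquired during the 4 loading doses (study visit 2".

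Section 9.6 repeats both rules. Neither section defines a baseline scan or exempts one from the exclusion.

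**The concern.** The plan collects a scan in study visit 2 so that change in size can be measured, and then excludes study visit 2 data from the efficacy analyses. This is a conflict between two stated rules, not just missing detail. In a single-arm study of about 10 subjects, within-subject change is the only evidence on size, so the choice of baseline scan matters for each subject affected.

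Timing is a second gap. If the scan is kept but was taken late in the loading period, it is no longer a pre-treatment measurement. Any early change on drug would be missed, or bleeding into the lesion during loading would count as baseline size. Without a written rule, the baseline would have to be chosen once the data are in hand, and a scan taken on drug cannot be replaced later by a pre-dose one.

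**Working it through.** The plan has no figure to reproduce here. The sample size of about 10 rests on feasibility, and 9.1 plans descriptive statistics only. The check is a comparison of sections plus a day count.

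**1. Does the exclusion reach the scan?** The scan is placed in study visit 2 (synopsis, 3.1.2, 6.10, 7.2). The exclusion covers data acquired during the loading doses and equates that period with study visit 2 in parentheses. It applies to the parameters listed in 9.5, which include size. On the literal text, the scan is excluded. It is not in the stated comparator either: by 3.1.1 a subject is enrolled after successful screening and then receives the loading doses, so a scan taken during visit 2 dosing is not in the pre-enrollment file.

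**2. Is the scan required before the first dose?**

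- 3.1.1 and 7.1 (screening): earlier scans are documented; no new scan is listed.
- 7.2.1 (Day -1): deals only with stopping bypassing-agent prophylaxis.
- 7.2.2.1 (Day 0, pre-treatment): names "Banked plasma sample [baseline antidrug antibody levels for Hemlibra (emicizumab)] for testing at the central laboratory" but no imaging.
- 7.2.3.1, 7.2.4.1 and 7.2.5.1 (Days 7, 14 and 21): no imaging item.
- Appendix 2: the tables for visits 1 and 2 have no CT/MRI row; the row first appears in the table of month 3 to 24 visits, marked at months 12 and 24. Some marks in the visit 1 and 2 tables look displaced in the copy reviewed, so I rely on the row labels only.

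No list requires or schedules the scan before dose 1.

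**3. How late could a compliant scan be?** The last loading dose is on Day 21 with a window of ±2 days, so up to Day 23. As a share of the year to the month 12 scan:

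- 21 / 365 = 5.8%
- 23 / 365 = 6.3%
- 28 / 365 = 7.7%, if the visit is taken to run its full 4 weeks

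**4. How many subjects?** Let k be the number who need a visit 2 scan. The documents do not give k, so I take the full range of 0 to 10. Under the literal exclusion, 10 − k subjects keep a usable recent baseline:

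| k (assumed) | 10 − k |
|---|---|
| 0 | 10 |
| 3 | 7 |
| 5 | 5 |
| 10 | 0 |

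**5. The trigger differs between sections.** In the synopsis and 3.1.2 a new scan is due if the existing one is older than one month *or* inadequate. In 6.10 and 7.2 it is due if the existing one is older than one month *and* unsuitable. A subject with a recent but inadequate scan, or an adequate but older one, is rescanned under the first rule and not under the second. So k depends on which section a site follows.

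**The case against.** The other side has four good arguments.

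- **A pre-dose scan is probably intended.** In 3.1.2 the scan sentence directly follows one that sets the antibody sample before the first loading dose, and it says the scan will also be obtained. The synopsis lists the scan before its weekly dosing items. Day -1 and the Day 0 allowance for other diagnostic procedures leave room for it. A reader might infer that no opportunity exists before the first dose; the documents do not support that. What stands is narrower: the pre-dose timing is attached explicitly only to the antibody sample, and the Day 0 allowance recurs on Days 7, 14 and 21, so it fixes no date.
- **The exclusion was probably aimed at events during loading.** A scan taken before dose 1 is arguably not acquired during the loading doses, and 6.10 collects it expressly to follow size. An analyst might well keep it. But the parenthesis in 9.5 covers the whole visit, and nothing in Section 9 says otherwise.
- **The scope is limited.** A reader might infer that the size endpoint loses its baseline altogether. It does not. Subjects with an adequate scan from within one month are untouched, and entry requires radiologic confirmation, so everyone has some earlier scan. For affected subjects, however, that scan is one the protocol itself treats as too old or inadequate.
- **No bias has been shown.** Four loading doses total 4 × 3 = 12 mg/kg, equal to 12 / 1.5 = 8 maintenance doses. A reader might take this as a measure of distortion, but it says nothing about lesion size, and the documents give no rate of size change over three weeks.

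The two harms are also alternatives: a scan dropped under 9.5 cannot also serve as an on-drug baseline.

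**Conclusion.** The point holds for subjects who need a visit 2 scan, from 0 to about 10 of about 10. Followed as written, 9.5 and 9.6 remove that scan and leave an older or inadequate one as baseline for a primary endpoint. Separately, pre-dose timing is suggested but not required, so a compliant scan could come up to 21 to 23 days after the first dose, about 6% of the interval to month 12. The direction and size of any bias cannot be estimated from the documents.

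This rests on a literal reading of the exclusion and on the absence of a baseline definition elsewhere in Section 9. Because the study is small and descriptive, the effect is confined to some subjects and the likely intent is sound, I rate it as something that should be fixed. The conclusion does not extend to the endpoint as a whole.

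**What to change.** 1. **Timing.** In 7.2, 7.2.2.1 and Appendix 2 (one new row), state that the baseline CT or MRI, where required, is completed before the first loading dose.
2. **Analysis.** In 9.5 and 9.6, limit the exclusion to bleeds, hospital admissions, anemia events and hemostatic therapy with onset from the first loading dose to the end of study visit 2. State that baseline assessments obtained before the first dose are retained. Define the baseline scan as the last adequate scan before the first dose. Flag any scan taken after dose 1 and report those subjects separately.
3. **Trigger.** Use one condition for the new scan in the synopsis, 3.1.2, 6.10 and 7.2.

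The cost is wording and one table row; no sample-size figure changes. Imaging would have to be booked within the existing screening window of up to 10 days. The number of scans changes only through item 3: the *or* condition calls for at least as many as the *and* condition. For any subject already dosed, item 1 comes too late, and the definition and flag in item 2 do the work.
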